7.1.5 Selection of subjects

7.1.5.1 Inclusion criteria (only those who meet all the following criteria can be enrolled)

- (1) Age \geq 3 years, body weight \geq 10 kg;
- (2) Secundum left-to-right shunt ASD with hemodynamic significance;
- (3) Distance from the defect edge to coronary vein sinus, superior and inferior vena cava and pulmonary vein \geq 5 mm; to atrioventricular valve \geq 7 mm;
- (4) Atrial septum length (stretched diameter) $>$ diameter of left disk.

7.1.5.2 Exclusion criteria (those who meet any of the following criteria cannot be enrolled)

- (1) Patients of primum, venous sinus and unroofed coronary sinus ASD;

- (2) Patients with atrial septal defect ≥ 26 mm;
- (3) Patients with other structural heart diseases in addition to ASD;
- (4) Patients with complication of obstructive pulmonary arterial hypertension or Eisenmenger syndrome;
- (5) Patients with infective endocarditis;
- (6) Patients with hemolysis, hemorrhagic disease or unhealed ulcer within 1 month before implantation, or any contraindication to aspirin treatment (except those who can take other antiplatelet agents for 6 consecutive months);
- (7) Patients with thrombosis (especially in left atrium or left auricle) as shown by echocardiography;
- (8) Patients with known hypercoagulable state;
- (9) Patients who have undergone heart surgery in the past;
- (10) Patients allergic to PLLA;
- (11) Patients refusing to sign the informed consent form;
- (12) Patients who have poor compliance with disease-related treatment and poor cooperation with follow-up visits;
- (13) Patients that are in pregnancy or lactation, or planned for pregnancy or get a positive pregnancy test result during the screening period;
- (14) Patients that have participated in any clinical trial that may affect the evaluation of the device in this trial and not completed or withdrawn from the previous clinical trial within 3 months prior to this trial screening period;
- (15) Patients not eligible for this clinical trial (determined by the investigator).

7.1.5.3 Dropout Criteria and management

Subjects who have signed informed consent forms and are screened qualified quit the trial and fail to complete the observation period specified in the protocol are called dropout cases, regardless of when and why. The criteria for dropout are as follows:

- (1) For whatever reason, the subject is unwilling or impossible to continue the clinical trial, and requires to withdraw from the clinical trial.
- (2) Although the subject does not explicitly propose to withdraw from clinical trial, he/she no longer receive treatment and examination and loses to follow-up
- (3) The subject presents SAE, and the investigator judges that the subject should withdraw from the clinical trial.
- (4) The subject has poor compliance.

Dropout management: For all dropout cases, the summary form of clinical trial completion should be filled in the original records and the reasons for dropout should be analyzed. When the subject drops out, the investigator should contact the subject as much as possible, inquire the reason and record the last clinical symptom, and complete the evaluation items that can be achieved. If the subject withdraws from the trial due to AE, the investigator should take corresponding treatment actions according to the actual situation of the subject.

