7.1.5.7 Expected duration of participation of each subject

According to the requirements of the trial protocol, each subject should receive screening before operation (-30 to 0 day), sign the informed consent form after passing the screening, undergo implantation of Absnow™ absorbable ASD closure system, and carry out visits before discharge, 30 days, 90 days, 180 days, 360 days, 2 years, 3 years, 4 years and 5 years post operation. Any AE/SAE found in the subject during clinical trial should be observed until the end or keeping stable.

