8.6 Criteria and reason for trial termination based on statistics

- (1) This clinical trial plans to conduct an interim effect evaluation. All subjects will not receive further interventions after the device is implanted. An interim evaluation on the safety and efficacy will be conducted after the 360-day follow-up data post operation are obtained.
- (2) The results of interim effect evaluation do not affect the subsequent follow-ups (visits 6, 7, 8 and 9) and the final statistical analysis after the completion of the trial. Therefore, there is no need to set the criteria and reasons for trial termination.

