4. STATISTICAL CONSIDERATION

For continuous variables, the following will be listed: number of valid cases, mean, standard deviation, median, 25th and 75th percentiles, minimum value, and maximum value. The number of decimal places for the 25th and 75th percentiles, minimum, and maximum values will match the records in the database. The mean and median will retain one more decimal place than the raw data recorded in the database, while the standard deviation will retain two more decimal places than the raw data recorded in the database.

For categorical variables, data will be presented in frequency tables (frequencies and percentages). Percentages will be rounded to one decimal place. When the frequency is zero, only the frequency needs to be listed; the percentage may be omitted to distinguish it from non-

zero values. When calculating percentages, the number of subjects in the specified analysis population will serve as the denominator.

All hypothesis tests employ one-sided tests unless otherwise specified, with a statistical significance level of $\alpha=0.025$. Differences are considered statistically significant when $P<0.025$. All confidence intervals were calculated at the 95% confidence level. P-values were rounded to three decimal places. If $P < 0.001$, the value was output as “<0.001”. If $P > 0.999$, the value was output as “>0.999”.

All analyses in the safety evaluation are based on observed data, without considering data imputation. For table analyses based on the safety analysis set, all subjects receiving at least one treatment with the study device will be included in the analysis. However, for listing analyses, all subjects with safety evaluations will be included, even if they did not receive any trial treatment.

Unless otherwise specified, baseline data shall be defined as the last valid measurement taken before the implant procedure.

When multiple observation data points exist for the same examination at the same follow-up time point, the observation closest in time to the scheduled visit date will be designated as the primary analysis record for the relevant statistical analysis.

Statistical analysis was performed using SAS 9.4[®] software. Subject information and safety databases were exported and stored in SAS XPORT format.

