6.1.1. Treatment-emergent Adverse Events

All TEAEs will be summarized by System Organ Class (SOC) and Preferred Term (PT), and the incidence will be presented accordingly. At each level of summarization, if a subject experiences one or more adverse events within a given category, the subject will be counted only once and will not be counted repeatedly. All percentages will be calculated using the total number of subjects in the SS as the denominator.

If the relationship of an adverse event to the investigational device or the procedure is unclear, it will be classified as related for analysis purposes. In the categorization of relationship to the investigational device or procedure, events assessed as possibly related, probably related, or definitely related will be grouped as related, whereas events assessed as not related or unlikely related will be grouped as unrelated.

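### Two of the four dropout criteria end scheduled observation of an implanted subject without withdrawn consent or loss to follow-up, and under the SAP each such exit before complete 360-day data can become an avoidable imputed failure

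*Protocol*

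**What the plan says.** Protocol 7.1.5.3 defines dropouts as screened, consented subjects who quit and "fail to complete the observation period specified in the protocol are called dropout cases, regardless of when and why". It then lists four criteria. The first two are the subject's own withdrawal and loss to follow-up. The other two are:

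- criterion (3): "The subject presents SAE, and the investigator judges that the subject should withdraw from the clinical trial";
- criterion (4): "The subject has poor compliance".

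Criterion (3) leaves the decision to the investigator. Criterion (4) gives no threshold and does not say who decides. At dropout the investigator is to try to reach the subject, "inquire the reason and record the last clinical symptom, and complete the evaluation items that can be achieved".

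Protocol 7.1.5.7 adds that "Any AE/SAE found in the subject during clinical trial should be observed until the end or keeping stable". Protocol 8.6 confirms the one-off nature of treatment: "All subjects will not receive further interventions after the device is implanted". The visit schedule (Protocol 7.2.2) plans echocardiography, ECG and adverse event review at every visit to 5 years, with common complications recorded to day 360.

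On analysis, SAP 4.2, 5.1.1 and 5.1.2 impute a missing 360-day result as ineffective closure and incomplete 360-day safety follow-up as a common complication. For the rest of safety, SAP 4 states: "All analyses in the safety evaluation are based on observed data, without considering data imputation". SAP 6.1.1 adds: "All percentages will be calculated using the total number of subjects in the SS as the denominator".

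**The concern.** Once the occluder has been released there is no continuing study treatment to stop, so withdrawal under criterion (3) or (4) acts mainly on data collection. Because these criteria stand beside withdrawal by the subject and loss to follow-up, they can reach a subject who still consents and could still be seen.

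Two things are at stake. First, a day-360 result that could have been measured is replaced by an assumed failure on both co-primary endpoints, and the decision rule tolerates very few of these. Second, the yearly visits from 2 to 5 years exist to observe an absorbable implant over time. Some subjects with an eventful course would not be observed there, yet they remain in the denominator of the adverse event rates.

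**Working it through.** **1. The plan's own figures.** Protocol 8.2.1 uses a one-sample z test with one-sided alpha 0.025 and power 80%: safety null 6% against 1%, efficacy null 94% against 99%. Both give

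n = [1.960·√(0.06·0.94) + 0.842·√(0.01·0.99)]² / 0.05² = 120.65, rounded up to 121.

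This matches the plan. The enrolled number is 121 × 1.2 = 145.2, rounded up to 146, which leaves 146 − 121 = 25 subjects as the dropout allowance. The SAP (3.1) plans 142, so both totals are used below.

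**2. How many failures the decision rule tolerates.** SAP 5.1.2 requires the exact two-sided 95% upper limit to lie below 6%. With x events in N, that limit is the 0.975 quantile of a Beta(x+1, N−x) distribution.

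| N | Events | Upper limit | Goal met? |
|---|---|---|---|
| 142 | 2 | 5.00% | yes |
| 142 | 3 | 6.05% | no |
| 146 | 3 | 5.89% | yes |
| 146 | 4 | 6.87% | no |

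The efficacy rule (lower limit above 94%) is the mirror image, so the same failure counts apply: 3 ineffective of 142 gives a lower limit of 93.95%, and 4 of 146 gives 93.13%.

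**3. Effect of withdrawals before complete 360-day data.** The FAS includes a successfully implanted subject with at least one later primary-endpoint observation. Complications are already recorded before discharge, so such a subject would normally be in the FAS and be imputed. Let w be the number withdrawn whose triggering event is not itself a listed complication, and let the remaining N − w have a true 1% rate (the plan's target). The goal is met if the observed events do not exceed c − w, where c = 3 for N=146 and c = 2 for N=142. The chance of this is P[Bin(N − w, 0.01) ≤ c − w].

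| w | N=146 | N=142 |
|---|---|---|
| 0 | 94% | 83% |
| 1 | 82% | 59% |
| 2 | 58% | 24% |
| 3 | 24% | 0% |
| 4 | 0% | 0% |

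For example, with w = 3 and N = 146 no observed event is allowed: 0.99^143 = 0.238. These are chances for the safety endpoint alone. If the SAE that led to withdrawal is itself a listed complication, the subject is already a safety event and imputation adds nothing there. A missing day-360 echo would still count as ineffective.

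**4. Other safety rates.** SAP 6.1 and 6.1.1 count subjects, once per category. Taking each route in turn:

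- *Overall SAE rate, criterion (3).* The subject has had an SAE and is already in the numerator. Later SAEs do not change the rate.
- *Device-related AE rate, criterion (3).* If the triggering SAE was related, or of unclear relation (which the SAP classes as related), the subject is already counted. A first device-related AE after an unrelated SAE is missed.
- *Rates by system organ class and preferred term.* New kinds of event after withdrawal are missed.
- *Criterion (4).* No earlier event is implied, so any first event after withdrawal is missed.
- *Echocardiography and ECG from 2 to 5 years.* Not obtained on either route.

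In each case of loss the subject stays in the safety set denominator. The documents do not say how many subjects criteria (3) and (4) would affect, so no size can be put on this part.

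**The case against.** The strongest reply is that the SAP already protects the primary endpoints: with missing counted as failure, a withdrawal cannot make the FAS result look better and only penalises the sponsor. That stands, and it is why the point about the primary endpoints is lost information and lost power, not a false claim of success. It depends on the SAP's rule being used. Protocol 8.7.2 instead carries the last observation forward for the main indicators and leaves safety endpoints unimputed; the two texts need reconciling.

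The opening definition in Protocol 7.1.5.3 requires that a subject actually quits, so one missed visit does not clearly make a dropout. Contact is to be attempted as far as possible, known events are followed until stable, and each dropout is described (Protocol 8.7.2). This softens the rule, but none of it keeps the scheduled visits.

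A reader might infer three stronger things that the documents do not support:

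- *That withdrawal after an SAE lowers the reported SAE rate.* It does not, since each subject is counted once and that SAE is already in. Nor can the plan's 20% dropout figure be used to size the loss: it covers all causes, most of which the proposed change would leave in place.
- *That the subjects lost are those most likely to have further device events.* This is plausible but undocumented. An SAE includes any hospitalisation, need not concern the device, and may have led to its removal (Protocol 13.1.4.1 foresees removal or retrieval).
- *That the investigator may end follow-up for poor compliance.* Only criterion (3) names the investigator.

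**Conclusion.** The point holds as a correctable design weakness. Criteria (3) and (4) allow scheduled observation to end for a subject with a one-off implant who has neither withdrawn consent nor been lost, and no section of either document restores it.

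The measurable cost is on the co-primary endpoints. Three imputed failures (N=142) or four (N=146) miss the safety goal with no observed complication, and the same counts miss the efficacy goal. One avoidable withdrawal costs about 12 percentage points of the chance of meeting the safety goal at N=146 (94% to 82%) and about 24 at N=142 (83% to 59%). These figures assume a true 1% rate in those observed, imputation as in the SAP, and withdrawals that were not already safety events.

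The cost to the remaining safety data is real but narrower, and cannot be sized: some first device-related events, new event types, events after criterion (4) withdrawals, and long-term imaging.

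**What to change.** In Protocol 7.1.5.3, remove criteria (3) and (4) as reasons to leave the study. State that every subject treated with the device stays in scheduled follow-up (day-360 echocardiography, complication checks, adverse events, yearly visits) after an SAE or missed visits, and becomes a dropout only on withdrawal of consent, loss to follow-up or death. For a subject who declines visits but allows use of data, collect vital status, re-intervention and any routine echocardiogram from medical records.

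This concerns observation only and changes no treatment rule or right to withdraw. It adds no scheduled visit or procedure. The cost is an amendment to the wording, plus effort at sites, which must keep trying to see less compliant subjects.

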7.1.5.4 Trial termination criteria

Trial termination means that the clinical trial is not ended according to the protocol and discontinued halfway. The main purpose of termination is to protect the rights and interests of subjects and ensure the quality of trial. In addition to the Article 5 mentioned below, the sponsor and the investigators should jointly negotiate whether to terminate the trial:

- (1) The trial should be terminated timely due to serious safety problems found during the trial;
- (2) The trial should be terminated timely because the product is found to be of no clinical value during the trial;
- (3) Major error is found in the protocol during the trial, which makes it difficult to evaluate the product safety and efficacy; Or serious deviation occurs during the implementation of the protocol and further continuation of the trial will make it difficult to evaluate the product safety and efficacy;
- (4) Clinical trial institutions and investigators do not comply with the relevant laws and regulations of the clinical trial and the clinical trial protocol, which are not corrected after being pointed out, or are serious, or continue to be unchanged;
- (5) National Medical Products Administration ordered the termination of clinical trial for some reasons.

From the perspective of protecting the rights and interests of the subjects, the investigators should continue to provide appropriate treatments for the subjects after the trial termination, and inform the subjects in detail of the management and related treatments received during the trial. The relevant data of the subjects can still be used to evaluate the safety of the product, and the termination of the trial should be timely fed back to the sponsor.

7.1.5.5 Enrollment time

It is estimated that the first subject will be enrolled in Aug 2018. Each clinical trial institution is expected to enroll three subjects every month, with a total time of six months for subject recruitment.

7.1.5.6 Expected clinical trial duration and determination basis

The total duration of this trial is five years and six months, and 146 subjects are planned to be enrolled within six months. After completing the 360-day visit data post operation, the interim statistical analysis report and the interim clinical trial report should be finished. And the registration application should be submitted to the NMPA. Then the follow-up of 2-5 years post operation will still be carried out continuously (once a year).

7.1.5.7 Expected duration of participation of each subject

According to the requirements of the trial protocol, each subject should receive screening before operation (-30 to 0 day), sign the informed consent form after passing the screening, undergo implantation of Absnow™ absorbable ASD closure system, and carry out visits before discharge, 30 days, 90 days, 180 days, 360 days, 2 years, 3 years, 4 years and 5 years post operation. Any AE/SAE found in the subject during clinical trial should be observed until the end or keeping stable.

7.1.5.8 Number of subjects required for clinical trial

Sample size: 146 cases

7.1.6 Efficacy evaluation method

7.1.6.1 Primary efficacy endpoint and corresponding evaluation, recording and analyzing method and time

Effective closure rate at 360-day post operation

Evaluation time: 360-day post operation

Definition of effective closure: no or only mild-small residual shunt (judging from left-to-right Doppler signal, left-to-right shunt signal with diameter < 5 mm) observed by TTE or TEE after device implantation.

Evaluation method: TEE or TTE

7.1.6.2 Secondary efficacy endpoint and corresponding evaluation, recording and analyzing method and time

Immediate operation success rate

Evaluation time: Immediately post operation

Immediate operation success means that left and right disks are effectively fixed on left and right sides of atrial septum respectively and smoothly released without displacement or migration and the delivery system is successfully withdrawn;

Note: the displacement and migration can be judged by observing whether the position of markers is the same as that before release under DSA, and whether the left and right discs are located on both sides of the atrial septum under TEE or TTE.

7.1.7 Safety endpoints and corresponding evaluation, recording and analyzing method and time:

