13.1.4 Possible AEs in this trial and corresponding treatments

13.1.4.1 Common complications and corresponding treatments

- (1) Occluder dislocation: Preoperative multi-sectional measurements of ASD size are helpful for selection of indications and occluders. Improper selection of occluder can easily cause dislocation. Through observing the position of the development site and the shape of the left and right discs of the occluder by TTE combined with chest X-ray, it can be judged whether the occluder falls off. If the occluder falls off, it should

be taken out with catcher. If the occluder is large or difficult to take out, the emergency surgery should be performed.

- (2) High-grade atrioventricular block: If degree III atrioventricular block occurs during the operation and is still not recovered after long-term suspension of operation, the interventional therapy should be abandoned; Drug treatment should be given in time if degree III atrioventricular block occurs after operation. The device should be removed by surgery and ASD should be repaired if the drug therapy is ineffective;
- (3) Cardiac tamponade: Cardiac tamponade can be judged by TTE. Emergent pericardial puncture should be performed for blood drainage and decompression to relieve tamponade, temporarily change the hemodynamics, and contend for rescue time. Meanwhile, saline and blood should be infused to correct hemorrhagic shock. Furthermore, emergency thoracotomy exploration should be prepared. Strict anesthesia management is required and cardiac arrest should be strictly prevented. Sufficient blood should be replenished. Blood accumulated in pericardium cavity should be removed during operation. Normal systolic and diastolic function of heart should be restored. Heart damage should be repaired accurately. Close monitoring of cardiac function and rational application of cardiovascular active drugs are required after operation;
- (4) Air embolism: It can be judged by TTE combined with chest X-ray. Oxygen should be inhaled immediately, atropine should be given to patients with slow heart rate, and nitroglycerin should be adopted at the same time to prevent vasospasm;
- (5) Residual shunt above medium: It can be judged by TTE. If the diameter of residual shunt is larger than 5 mm and has hemodynamic significance, it is recommended to block the residual shunt again;

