5.1.1. Primary efficacy endpoints

Primary efficacy endpoint is effective closure rate at 360-day post operation. Effective closure is defined as no or only a trivial to small residual shunt (based on left-to-right Doppler flow signals with a diameter <5mm) as assessed by TTE or TEE after device implantation.

For the primary efficacy endpoint evaluation, the following hypotheses are tested:

Null hypothesis $H_0: \pi_1 \leq \pi_0$. That is, the Absnow Absorbable Atrial Septal Defect Occluder System fails to meet the design requirement for the 360-day post-operation effective closure rate.

Alternative hypothesis $H_1: \pi_1 > \pi_0$. That is, the Absnow Absorbable Atrial Septal Defect Occluder System meets the design requirement for the 360-day post-operation effective closure rate.

π_1 refers to the expected 360-day post-operation effective closure rate, π_0 refers to the Objective Performance Criteria (OPC) value of 360-day post-operation effective closure rate

Statistical inference will be performed using the exact method to estimate the 95% confidence interval (CI) for the effective closure rate at 360 days post-operation, as well as the P-value for comparison with the predefined performance goal of 94%. If the lower limit of the two-sided 95% CI for the effective closure rate at 360 days exceeds 94%, the null hypothesis will be rejected, and it will be concluded that the Absnow Absorbable Atrial Septal Defect Occluder System meets the

design requirement for the 360-day post-operation effective closure rate. Otherwise, it cannot be concluded that the 360-day effective closure rate meets the predefined performance requirement.

If a subject has missing valid data at 360 days, the subject will be imputed as “ineffective” using the Non-responder Imputation (NRI) method. For analyses based on the PPS, missing data will not be imputed.

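### Effective closure is scored from the day-360 echo alone, so a defect closed by a later procedure can count as closure by the study device; the efficacy rate is exposed, the joint verdict much less so

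*Protocol*

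**What the plan says.** **Endpoint.** Protocol 7.1.6.1 defines effective closure as "no or only mild-small residual shunt (judging from left-to-right Doppler signal", where the signal must be under 5 mm on either form of echocardiography, and it fixes a single time point: "Evaluation time: 360-day post operation". SAP 5.1.1 uses the same shunt-only criterion: "Effective closure is defined as no or only a trivial to small residual shunt", below 5 mm, "as assessed by TTE or TEE after device implantation". Neither text requires that the study device still be in place or that it alone closed the defect.

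**Rescue procedures foreseen.** Protocol 13.1.4.1 describes three:
- for a residual shunt over 5 mm with haemodynamic significance, "it is recommended to block the residual shunt again";
- for third-degree atrioventricular block after operation, "The device should be removed by surgery and ASD should be repaired if the drug therapy is ineffective";
- for a displaced occluder, retrieval, and "If the occluder is large or difficult to take out, the emergency surgery should be performed".

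**Analysis sets.** The FAS is the primary set (SAP 5.1). Limb (a) keeps subjects who had immediate success and one later observation. Limb (b) keeps subjects whose implantation failed because of the device, whether or not a device remains in the body (protocol 8.9, SAP 4.1.1). Protocol 13.3.2 foresees one such case: a locking piece that fails during the operation, with the device reclaimed or taken out.

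**Missing data.** SAP 4.2 imputes failure on both co-primaries after withdrawal or missing day-360 data. Protocol 8.7.2 carries the last observation forward for the main indicators. Neither rule is triggered by a rescue procedure.

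**The concern.** The objective in protocol 7.1.1 concerns closure by the absorbable system, but the scoring rule records only the state of the septum at day 360. A second occluder or a surgical repair can give a clean echo after the study device has failed or been taken out. Under the literal rule that subject is a success.

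Two things are at stake. First, efficacy has its own hypothesis, exact interval, P-value and conclusion (SAP 5.1.1), and protocol 8.1 calls it the high-priority index. The closure rate goes into the 360-day report that supports the registration application, and a safety event recorded for the same subject does not correct it. Second, if the rescue had a cause outside the seven listed complications, the subject may count against neither co-primary. With so few failures allowed, how such a subject is scored should be settled before the data are seen.

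**Working it through.** **Inputs.** OPC 94% and target 99% for closure, OPC 6% for complications, one-sided alpha 0.025, power 80% (protocol 8.2.1, 8.3). Planned size is 146 in the protocol and 142 in the SAP (3.1). The decision rule is the exact two-sided 95% interval (SAP 5.1.1, 5.1.2). I assume every planned subject is in the FAS.

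**1. The plan's own figure.** One-sample z test with null variance in the test statistic:

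n = [(1.960 × √(0.94 × 0.06) + 0.8416 × √(0.99 × 0.01)) / 0.05]² = 120.65, so 121, with power 0.802. This matches the protocol. Its 146 is 121 × 1.2 = 145.2, rounded up.

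**2. Failures the exact rule allows.** The lower limit for x successes of n is the 2.5% quantile of Beta(x, n − x + 1). The safety upper limit is its mirror image.

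| N | Failures or events | Closure lower limit | Complication upper limit | Each test |
|---|---|---|---|---|
| 146 | 3 | 94.1% | 5.89% | pass |
| 146 | 4 | 93.1% | 6.87% | fail |
| 142 | 2 | 95.0% | 5.00% | pass |
| 142 | 3 | 93.95% | 6.05% | fail |

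**3. Weight of one subject.** 1/146 = 0.68 and 1/142 = 0.70 percentage points.

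**4. Rescue after a listed complication, N = 146.** Suppose three subjects have an open shunt of at least 5 mm at day 360, and a fourth was re-closed earlier for such a shunt and has a clean echo.
- As written, efficacy has 3 failures and passes (94.1%). Safety has 4 events, because the three open shunts are also listed complications, and fails (6.87%). The trial fails.
- With the fourth subject scored as a failure, efficacy fails too (93.1%). The trial still fails.

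The efficacy conclusion changes; the joint verdict does not.

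**5. Rescue for an unlisted cause, N = 146.** Replace the fourth subject by a limb (b) implantation failure, later closed by other means, with a clean day-360 echo and no listed complication.
- As written, efficacy has 3 failures (94.1%) and safety 3 events (5.89%). Both pass and the trial succeeds.
- With that subject scored as a failure, efficacy has 4 failures (93.1%). The trial fails.

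At N = 142 the same happens with two open shunts plus one such subject (95.0% against 93.95%).

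**6. Illustration for the efficacy test alone.** The documents give no rescue rate. Assume unaided closure equals the OPC of 94% and rescue adds d points. The chance of passing is P(X ≥ 143) with X ~ Bin(146, 0.94 + d), or P(X ≥ 140) with X ~ Bin(142, 0.94 + d).

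| d (points) | N = 146 | N = 142 |
|---|---|---|
| 0 | 2.2% | 0.8% |
| 1 | 6.3% | 2.5% |
| 2 | 16.1% | 7.4% |
| 3 | 35.9% | 19.8% |

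These are not probabilities of trial success, which also requires the safety test to pass.

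**The case against.** The strongest reply is that every rescue route in protocol 13.1.4.1 is already counted. Re-closure follows a shunt that is a listed complication, surgical removal follows a listed conduction block, and retrieval or emergency surgery follows displacement. Each is a primary safety event whatever a later echo shows. The safety limit mirrors the efficacy limit, and the SAP applies the same FAS and exact rule to both. This stands: on those routes safety fails no later than efficacy would, as step 4 shows. A reader might infer that one rescued subject generally reverses the trial's conclusion; the documents do not support that.

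A reader might also infer that every rescue inflates the closure rate. That is too strong. A subject who is withdrawn, or has no day-360 echo, is ineffective under SAP 4.2. Protocol 8.7.2 could instead carry a post-rescue echo forward, so the two rules need reconciling. The PPS may drop rescued subjects because of treatments that affect the efficacy evaluation, but it is secondary and does not count them as failures.

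Device thrombosis, named in protocol 6.3.1, may look like the obvious unlisted cause. It is a thin example: that section asks only for closer follow-up, and no passage foresees device removal for it.

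Finally, the objective and the analysis text attribute the closure rate to the study system, and the words about assessment after implantation can be read as excluding other means of closure. That reading is possible, and no sentence says outright that a rescued subject succeeds. But no scoring rule states the exclusion either, and a co-primary endpoint should not depend on it. Whether removal of a device that had closed the defect is a closure failure is a choice of estimand, which is a reason to write the choice down.

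**Conclusion.** The point holds for the efficacy endpoint as reported and tested. Under the literal definition, a FAS subject with a day-360 shunt under 5 mm counts as effectively closed even if the defect was re-closed or repaired, or the device was removed or never left in place. Each such subject adds about 0.7 points, and the efficacy test allows at most 3 failures of 146 or 2 of 142.

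The joint verdict is largely protected on the routes the protocol foresees for listed complications. It is exposed only for causes outside the seven, most plausibly a device-caused implantation failure under FAS limb (b) later closed by other means. How often that would happen cannot be taken from the documents. The conclusion rests on the literal definition and on the absence of any re-intervention rule, and the counts assume all planned subjects are in the FAS.

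**What to change.** Add one sentence to protocol 7.1.6.1 and SAP 5.1.1: in the FAS, any repeat closure or surgical repair of the treated defect, or absence or removal of the study device, before the day-360 assessment is scored as not effectively closed, whatever the later echo shows. Report scoring by the day-360 echo alone as a sensitivity analysis. Reconcile the missing-data rules in protocol 8.7.2 and SAP 4.2 so that a post-rescue echo cannot be carried forward as a success.

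The cost is a sentence in each document and one extra analysis. The closure rate may be slightly lower. This is an endpoint-scoring rule and changes no patient care.
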